12.1.1 Previous / Concomitant therapies date imputation

The following imputation of partial dates is made:

Previous therapies: Impute partial start date with lower limit, and partial end date with minimum of upper limit and study treatment start date – 1. Missing dates are not imputed.

Study concomitant therapies ongoing at study treatment start: Impute partial start date with lower limit and partial end date with upper limit. Missing dates are not imputed.

Study concomitant therapies not ongoing at study treatment start: Impute partial start date with maximum of lower limit and study treatment start date, impute partial end date with upper limit. Missing dates are not imputed.

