5.2.5.5 Disease modifying therapies for MS (DMTs)

Disease modifying therapies are defined as therapies which can favorably alter the course of the disease by reducing the rate and severity of relapses or delaying disease progression by preventing accumulation of disability. For this statistical analyses, DMTs will be identified on an ingredient level if containing any of the text indicated in [Table 5](#) below. Medications in ATC class S (sensory organs, i.e., ophthalmologicals and/or otologicals) will not be considered.

In addition, any other potential DMT, i.e. medications with preferred drug name “INVESTIGATIONAL DRUG” or “BLINDED THERAPY” for Multiple sclerosis (recorded either on the ‘Study-treatment-concomitant therapy - Disease-modifying’ or ‘MS Specific Treatment History Log’ eCRF) will also be taken into account.

Table 5 Disease modifying therapies for MS

ALEMTUZUMAB	MITOXANTRONE
AZATHIOPRINE	MYCOPHENOLIC ACID
CERALIFIMOD	NATALIZUMAB
CICLOSPORIN	OCRELIZUMAB
CLADRIBINE	OFATUMUMAB
CYCLOPHOSPHAMIDE	OZANIMOD
DACLIZUMAB	PEGINTERFERON BETA-1A
DIMETHYL FUMARATE	PLOVAMER
FINGOLIMOD	PLOVAMER ACETATE
GLATIRAMER ACETATE	RITUXIMAB
INTERFERON BETA-1A	SECUKINUMAB
INTERFERON BETA-1B	TERIFLUNOMIDE
LAQUINIMOD	SIPONIMOD
METHOTREXATE	IMMUNOGLOBULINS NOS
INTERFERON ALFA	ETRASIMOD

A text search in ingredients will be conducted: Include all medications containing any of the text above to ensure salts (e.g., “Fingolimod Hydrochloride”) and combination therapies are included.

Start of alternative DMTs for MS (required for efficacy analysis):

For each subject receiving study concomitant DMTs the start date is defined as the first start date of any study concomitant DMT.

Imputation of partial start date is detailed in Section 12.1.1. Missing start dates will not be imputed, consequently therapies with missing start date will not be considered in efficacy analyses up to start of alternative DMTs for MS.

Note on previous DMTs: Occurrence of previous DMTs (stopped prior to ICF consent) is assessed systematically (Yes/No tick boxes) in the ‘MS Specific Treatment History’ eCRF for selected medications. However, for reporting purposes, medications are identified via coding as specified above. On the ‘MS Specific Treatment History Log’ the ‘reason for discontinuation’ (free text) is collected and will be included in listings of MS specific therapies.

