9.4.5.4 Therapies used for accelerated elimination

Therapies used for accelerated elimination started between EOT and EOT + 15 days are summarized in the same way as for treatment concomitant therapies on the FAS. A listing of therapies used for accelerated elimination on the FAS is prepared.

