9.6 Analysis of the primary efficacy variable

9.6.1 Primary estimand

The primary estimand, the target for estimation in this study, is defined by the following components:

Population: Subjects with relapsing multiple sclerosis (RMS), as defined by the inclusion/exclusion criteria from the study.

Variable: ARR (number of confirmed relapses per subject-year) up to EOS, with EOS being at least 108 weeks after randomization [see Section 5.4.1].

Intercurrent events with corresponding strategies:

- **Treatment discontinuation:** Treatment Policy Strategy; including all confirmed relapses regardless of treatment discontinuation.

- **Start of alternative DMTs for MS:** Treatment Policy Strategy; including all confirmed relapses, regardless of start of alternative DMTs. Note: As per protocol alternative DMTs for MS are only allowed to be started after treatment discontinuation, therefore this intercurrent event is not expected to occur prior to or independent from treatment discontinuation.
- **Study discontinuation:** Hypothetical Strategy; effect if all subjects remained on study as planned per protocol. The assumptions for handling study discontinuation are detailed for the main analysis in Section 9.6.3 and for the sensitivity analyses on premature study withdrawal in Section 9.6.4.3.

Summary Measure: Rate ratio of ponesimod versus teriflunomide.

The primary analysis will be based on the Full Analysis set [see Section 7.1.2].

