9.6.5.3 ARR based on all relapses up to EOS on the FAS

Same analysis as for the main analysis, but with number of all relapses up to EOS as a response variable. All other aspects of the model are as per the main analysis. This analysis is described to check the consistency of the treatment effect on all relapses and that no bias was introduced in the confirmation of relapses.

The following sensitivity analysis is conducted

- *ARR based on all relapses up to EOS including derived stratification variable:* Same analysis as for the main analysis, but instead of adjusting for the stratification variables from IRT adjust for eCRF-derived stratification variables.

9.6.5.4 ARR based on confirmed relapses up to start of new DMT for MS on the FAS

Same analysis as for the main analysis, but with number of confirmed relapses up to the minimum of EOS date, or the start of a new DMT for MS as a response variable, and the logarithm of time (in years) between randomization and the Min (EOS date, start of a new DMT for MS) as an offset variable. By checking the consistency of the treatment effect in this analysis with the effect observed in the main analysis, we evaluate whether a bias in evaluating the treatment effect has been introduced in the FAS analysis due to the decision to start a DMT.

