12 HANDLING OF MISSING/INCOMPLETE DATE AND TIME FIELDS

In the following, ‘lower limit’ and ‘upper limit’ refer to the minimum or maximum, respectively, of a possible date. For example, if the day is missing, the lowest limit is the first day of the given month and the upper limit is the last day of the given month. If the day and month are missing, the lower limit refers to the first day of the given year and the upper limit to the last day of the given year. *The earliest and the latest dates refer to the first or last date, respectively, when ordered in sequence.*

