12.1 Previous / Concomitant therapies

For previous and concomitant therapies with missing or partial start and end dates the following rules for assignment to previous therapies and study concomitant therapies are applied [see [Table 11](#)].

Table 11 Handling of missing or partial start and end dates for previous/concomitant therapies

eCRF page	Start date	End date	Previous / Concomitant
Prev*	Unless start date clearly after/on STS (Start date either: prior to STS date, partial with either lower or upper limit prior to STS date, or missing)	Unless end date after/on STS (Either prior STS, partial with either lower or upper limit prior STS, or missing)	Previous
Con**	Unless start date clearly after/on STS (as above)	Prior to STS date; or Partial with upper limit prior to STS date;	Previous
Con**	Start date confirmed prior STS (Start date either: prior to STS date, partial with upper limit prior to STS date)	End date on STS date and 'Ongoing at start of Treatment' ticked 'No'; or Partial with lower limit prior to STS date and upper limit after/on STS date and 'Ongoing at start of Treatment' ticked 'No';	Previous
Any	All other cases not listed above	All other cases not listed above	Study concomitant

STS = Study treatment start; For subjects randomized but not treated the randomization date is used instead of the STS.

* Includes 'Previous Medications' or 'MS Specific Treatment History Log' eCRF: On these forms as per CRF completion guidelines only medications that stopped prior to signature of informed consent are to be recorded.

** Includes all forms collecting therapies apart from 'Previous Medications' or 'MS Specific Treatment History Log' eCRF.

To derive treatment concomitant therapies in case of missing or partial start dates for a study concomitant therapy the following rules apply:

- Start date is available and after EOT, or start date is partial with lower limit after EOT: not considered treatment concomitant irrespective of end date
- Start date is available and prior or on EOT, start date is partial with lower limit prior or on EOT, or start date is missing: considered treatment concomitant irrespective of end date
- Subjects randomized but not treated are not considered to have any treatment concomitant medications

To further flag study concomitant therapies as 'ongoing at study treatment start' or 'started during study drug administration' medications the following rules apply:

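### Partial start dates of new MS therapies have no floor at the last dose, so the supplementary ARR up to start of a new DMT can lose on-drug follow-up and relapses

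*SAP*

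**What the plan says.** Section 5.2.5.5 defines the start of alternative DMTs for the efficacy analyses: "the start date is defined as the first start date of any study concomitant DMT". For incomplete dates it adds: "Imputation of partial start date is detailed in Section 12.1.1". Completely missing dates are not imputed.

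For study concomitant therapies not ongoing at treatment start, section 12.1.1 gives the rule: "Impute partial start date with maximum of lower limit and study treatment start date". Section 12 defines the limit: "if the day is missing, the lowest limit is the first day of the given month". If day and month are both missing, it is 1 January. EOT does not enter the rule.

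Section 9.6.1, on intercurrent events, notes that "alternative DMTs for MS are only allowed to be started after treatment discontinuation".

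The supplementary analysis in section 9.6.5.4 counts confirmed relapses up to "the minimum of EOS date, or the start of a new DMT for MS", with the log of the corresponding time as offset. Section 5.4.1.2.5 ends both the count and the follow-up on the day before the DMT start. Its stated purpose is to check whether the decision to start a DMT biased the full-analysis-set result.

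Separately, section 12.1 treats a study concomitant therapy whose partial start date has a lower limit on or before EOT as "considered treatment concomitant irrespective of end date".

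**The concern.** The SAP's own premise is that a new DMT follows the last dose. Its imputation rule ignores this and takes the earliest calendar day that the partial date allows, bounded only by the first dose. When EOT lies in the same recorded month or year, a switch made after EOT is dated inside the treatment period.

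The analysis exists to show whether switching distorted the primary result. A relapse shortly before a subject stops and switches is one that such a check needs to retain. Under the present rule that relapse, and the on-drug time around it, can fall after the imputed cut-off. The same partial date makes 12.1 flag the DMT as taken during study treatment, which would suggest on-treatment use that may not have occurred.

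**Working it through.** The SAP gives no figure to reproduce here, so the check applies its date rules to illustrative subjects.

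**Formulas**
- Present rule: imputed start = max(lower limit, first dose).
- Alternative: imputed start = max(lower limit, EOT + 1 day).
- Follow-up (5.4.1.2.5) = (day before imputed start − randomization) + 1.
- On-drug days lost = max(0, EOT − imputed start + 1).
- A relapse is lost if its onset is on or after the imputed start.

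**Examples.** Randomization and first dose are both on 10 Mar 2016 (section 2.1.1 places them on the same day). The relapse is on 12 Jun 2017 in a, b and d, and on 12 Sep 2016 in c.

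| Case | EOT | DMT start recorded | Present rule: start, follow-up | On-drug days lost | Relapse | Floor at EOT + 1: start, follow-up | Relapse |
|---|---|---|---|---|---|---|---|
| a | 20 Jun 2017 | Jun 2017 | 1 Jun 2017, 448 days | 20 | lost | 21 Jun 2017, 468 days | kept |
| b | 20 Jun 2017 | 2017 | 1 Jan 2017, 297 days | 171 | lost | 21 Jun 2017, 468 days | kept |
| c | 20 Sep 2016 | 2016 | 10 Mar 2016, 0 days | 195 | lost | 21 Sep 2016, 195 days | kept |
| d | 20 Jun 2017 | Jul 2017 | 1 Jul 2017, 478 days | 0 | kept | 1 Jul 2017, 478 days | kept |

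Case d shows that nothing on-drug is lost when the lower limit falls after EOT. If the relapse in case a had been on 20 May 2017, both rules would keep it. In case c, log(0) does not exist and the subject leaves the model. Section 10.1.1 itself notes, for its imputation model, that zero-time records are ignored for this reason.

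**How often a date would be affected.** This depends on the gap from EOT to DMT start, which the SAP does not give.
- Gap assumed 1-60 days: about 25% of month-and-year dates are affected, with a mean loss of about 10 on-drug days. For year-only dates it is about 92% and 169 days.
- Gap assumed 12-60 days, after the 11-day elimination procedure of section 2.1.1: about 12% and 7 days, and about 90% and 166 days.

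**Effect on the rate ratio (all inputs assumed).** Take 567 subjects per arm (about half of 1133), 2.0 years each, and ARR 0.30 on teriflunomide against 0.20 on ponesimod, a ratio of 0.667. Each affected subject loses 15 or 180 days and 0.3 to 0.9 relapses, the same in both arms. With k = 567 × share switching × share of dates partial:

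ARR = (true ARR × 1134 − k × relapses lost) / (1134 − k × days lost / 365.25)

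- Switching 10% in both arms, 20% partial, 180 days and 0.9 relapses lost: k = 11.34. Teriflunomide (340.2 − 10.206) / (1134 − 5.588) = 0.2924. Ponesimod (226.8 − 10.206) / 1128.412 = 0.1919. Ratio 0.656.
- Switching 15% on teriflunomide and 8% on ponesimod, otherwise the same: k = 17.01 and 9.07. ARRs 0.2886 and 0.1936. Ratio 0.671.

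Over the scenarios with 5-20% of dates partial, the ratio runs from 0.656 to 0.671. With 50% partial it runs from 0.640 to 0.678.

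**The case against.** The best defence is that the earliest possible date is a deliberate, conservative convention: no counted time can then fall under the new DMT. The SAP also does not treat on-treatment DMT use as impossible, since section 7.1.3 and deviation codes PD_MM.088 and PD_MM.093 provide for it. The second point stands, and the fix must leave room for recorded on-treatment starts. The first does not save the rule. The later of the lower limit and EOT + 1 is still the earliest day consistent with both the record and section 9.6.1. The SAP uses known sequence in this way elsewhere: partial diagnosis dates are floored at first symptoms (5.2.2), and partial EDSS dates at the day after the previous scheduled assessment (5.4.2.3.1).

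It is also fair to say that the effect is small and confined to one supplementary analysis, its forest-plot counterpart and descriptive tables. DMTs taken during the study have their own eCRF page, and nothing in the SAP suggests that year-only dates are common.

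Three stronger readings are tempting but unsupported:
- That relapses are removed preferentially in the arm with more switching, giving a predictable bias. The ratio moves away from 1 with equal switching and towards 1 with more switching on teriflunomide.
- That elimination agents are post-treatment by definition, so the table of "Therapies used for accelerated elimination started between EOT and EOT + 15 days" must be wrong. Section 5.2.5.8 identifies them by drug name, and PD_MM.094 foresees use during treatment.
- That a floor at EOT + 1 would return these DMTs to the table of those started after EOT + 7 days (9.4.5.1). It would not, because EOT + 1 is earlier than EOT + 7.

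**Conclusion.** The point holds in conditional form. The rule in 12.1.1 conflicts with the premise in 9.6.1, and no other section supplies a floor at EOT. Section 5.4.1.2.5 points to 5.2.5.4 for the definition, but that section only sends partial dates back to 12.1.

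On-drug time is lost only when the lower limit is on or before EOT: up to about 30 days with the day missing, and up to about a year with day and month missing. A relapse is lost only if its onset is on or after the imputed day. The zero-follow-up case needs a year-only date, with randomization and EOT both in that year.

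The primary ARR is untouched, because its estimand counts relapses regardless of DMT start. The overall size depends on the unknown number of partial dates. The rate-ratio ranges rest on assumed inputs and show a modest shift in either direction. The correction is still worth making, because the analysis is a check on switching and the remedy is cheap.

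**What to change.** In 12.1.1, add a rule for DMTs for MS that were not ongoing at treatment start. If the possible start range extends beyond EOT, and neither the eCRF nor a logged deviation (PD_MM.088 or PD_MM.093) shows an on-treatment start, impute the partial start date as max(lower limit, EOT + 1 day). Otherwise keep the present rule. Use this date in 5.4.1.2.5 and 9.6.5.4.

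Add the same exception in 12.1 to the treatment-concomitant flag and to the flag for therapies started during study drug administration. Changing 12.1.1 alone would leave a DMT dated EOT + 1 still labelled as on-treatment use.

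The cost is a sentence in 12.1.1, a matching exception in 12.1 and a small derivation change, using an EOT date that is already derived. The downside is that a true on-treatment start with an ambiguous date and no logged deviation would be dated slightly late.

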12.2 Relapse

Type of date/time	Date/time is incomplete	Date/time is missing
Relapse start date (collected on ‘Relapse Summary’ eCRF)	Maximum of lower limit and randomization date Unless upper limit is prior to randomization date, then upper limit	Randomization date

eCRF = electronic case report form.

12.3 Adverse event onset and death dates

The following imputation rules are applied for (partially missing) AE onset dates and (partially missing) dates of death:

- Onset day missing: If month and year is clearly on or after study treatment start (short: STS, the date of first study drug intake) month and year, and clearly before or on the month and year of last intake date + 15 days, consider the event as treatment-emergent. With regard to the date imputation, the following rules are applied:
 - If the record’s origin is the First-Dose eCRF and month and year correspond to month and year of STS, impute onset date and time as the date and time of the first study drug intake.
 - If the record’s origin is the First-Dose eCRF and month and year are clearly after STS month and year, but a date of re-initiation with corresponding month and year is documented, impute onset date and time as the date and time of this re-initiation study drug intake (in case more than one study drug re-initiations are

- documented in this month and year, impute with the date and time of the earliest of those).
- If the record's origin is the First-Dose eCRF and month and year are clearly after STS month and year, but no date of re-initiation with corresponding month and year is documented, the onset date is imputed to the 1st day of the month and year given and time to 00:00.
 - If the record's origin is the main CRF and month and year is clearly on or after STS month and year, the onset date is imputed as the maximum of (date of Treatment day 2, 1st day of the month and year given) and time is imputed to 00:00.
 - If event onset month and year is clearly prior to the STS month and year, the onset date is imputed to the last day of the given month (i.e., 28th, 29th, 30th, or 31st depending on month) and year and time is imputed to 00:00. This imputation is done irrespective of eCRF origin (First-Dose or Main).
- Onset day and month missing: If the year is the same year as the year of STS or later, and if the year is prior to or in the same year as the last intake date + 15 days, consider AE as treatment-emergent. With regard to the date imputation, the following rules are applied:
 - If the record's origin is the First-Dose eCRF and the year corresponds to the year of STS, impute onset date and time as the date and time of the STS.
 - If the record's origin is the First-Dose eCRF and the year is clearly after the year of STS, but a date of re-initiation with corresponding year is documented, impute onset date and time as the date and time of this re-initiation study drug intake (in case more than one study drug re-initiations are documented in this year, impute with the date and time of the earliest of those).
 - If the record's origin is the First-Dose eCRF and the year is clearly after the year of STS, but no date of re-initiation with corresponding year is documented, the onset date is imputed to January 1st of the given year and time to 00:00.
 - If the record's origin is the main CRF and year is clearly on or after the year of STS, the onset date is imputed as date of maximum of (Treatment day 2, January 1st of the given year) and time is imputed to 00:00.
 - If the event onset year is clearly prior to the year of STS, the onset date is imputed to 31-December of the given year and time is imputed to 00:00. This imputation is done irrespective of eCRF origin (First-Dose or Main).
 - Missing onset time is imputed to
 - the time of the STS, if the onset date equals the STS.
 - the time of the study drug intake at re-initiation, if the onset date equals the date of a documented study drug re-initiation.
 - 00:00, for any other onset date.

- Onset date is completely missing: Consider as treatment-emergent. The onset date and time is imputed as date and time of the STS (if death date or if AE onset date with record's origin is the First-Dose eCRF), if AE onset date with record origin in the main CRF, the onset date is imputed as Study Day 2.

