5.1.6 Subject study completion status

A subject is considered to have completed the study as per the corresponding entry on the 'End of Study' eCRF ("Did the subject complete the study?" answered with "Yes"). All subjects not completing the study are considered to have prematurely discontinued the study.

Note: A subject who prematurely discontinued study treatment but completed the PTOp is considered to have completed the study according to the protocol.

The End-of-Study (EOS) date is defined as the 'Date of End of Study' collected on the end of study eCRF, unless a subject is lost to follow-up or dies, in which case 'Date of Last Contact' from the end-of-study eCRF or 'Date of Death' from Death eCRF are used. If missing, the last recorded visit date (i.e., the latest assessment date within any visit) is considered as the EOS date.

For subjects completing the 108 weeks of treatment and entering the extension study, the EOS visit should occur at the FU1 visit (scheduled 14–22 days after last drug intake), or at the abbreviated FU2 visit if available (scheduled 23–37 days after last drug intake). For subjects completing the 108 weeks of treatment and not entering the extension study, the EOS visit corresponds to the FU2 visit (scheduled 30–37 days after last drug intake). For subjects prematurely discontinuing study treatment, EOS is scheduled to be the Week 108 visit (Visit 14A – W108A – Week 108).

For subjects prematurely discontinuing the study, reasons for premature discontinuation from study are: ‘Death’, ‘Lost to follow-up’, ‘Subject decision’ (further split into ‘Withdrawal of consent’, ‘Tolerability related’, ‘Efficacy related’, and ‘Other’), ‘Physician decision’ (further split into ‘Adverse event’ and ‘Other’) or ‘Sponsor decision’ (further split into ‘Study terminated’ and ‘Other’). Whenever ‘Other’ is selected, free text can be provided in addition. An additional category ‘Reason not provided’ is defined for subjects where the reason is missing.

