9.10.2 Deaths, other serious adverse events

9.10.2.1 Death

The number and percentage of subjects who died are summarized per treatment group, including the reported primary cause of death. A summary table is provided for all deaths

overall and split by time of death (treatment-emergent and more than 15 days after end of study treatment).

A separate listing including all deaths is provided based on the SCR; treatment-emergent deaths are flagged as such in that listing.

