12.4 Study treatment start and EOT

The following imputations of study treatment start and EOT are considered for assigning safety events and assessments to the treatment-emergent period and used for deriving efficacy variables with definitions requiring EOT date. It is not considered for derivation of exposure variables. Details for assigning safety events and assessments to the treatment-emergence period, as described in Section 5.5.1, apply.

Type of date/time	Date/time is incomplete	Date/time is missing
Study treatment start date	Maximum of lower limit and randomization date.	Randomization date
Study treatment start time	See missing.	0:00 or randomization time if study treatment start date (after imputation) is equal to randomization date.
EOT	Earliest between treatment start date + 756 days (108 weeks), the upper limit, EOS date, and Death date.	Earliest between treatment start date + 756 days (108 weeks), EOS date and Death date.

EOS = End of Study; EOT = End of Trial.

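### Section 12.3 imputes death dates with no floor at the last date known alive, so a subject seen alive off drug can be tabulated as a treatment-emergent death

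*SAP*

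**What the plan says.** Section 12.3 covers both kinds of date in one set of rules: "The following imputation rules are applied for (partially missing) AE onset dates and (partially missing) dates of death". Section 5.5.1 sends deaths to that section when it decides whether they are treatment-emergent, that is, from first dose up to and including EOT + 15 days.

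- **Completely missing death date.** The event is considered treatment-emergent, and "The onset date and time is imputed as date and time of the STS (if death date" is the rule that applies. STS is the first study drug intake.
- **Day missing, main CRF.** "the onset date is imputed as the maximum of (date of Treatment day 2, 1st day of the month and year given"). The event is treatment-emergent if its month is not before that of first dose and not after that of last intake + 15 days.
- **Day and month missing, main CRF.** "the onset date is imputed as date of maximum of (Treatment day 2, January 1st of the given year"). The same test is applied to the year.

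Three other places use a death date. Section 9.10.2.1 tabulates deaths "split by time of death (treatment-emergent and more than 15 days after end of study treatment"). Section 5.1.6 takes the Date of Death from the Death eCRF as EOS for a subject who dies, and adds: "If missing, the last recorded visit date (i.e., the latest assessment date within any visit) is considered as the EOS date". It does not say what happens when the date of death is only partial. Section 12.4 fills a missing EOT with "Earliest between treatment start date + 756 days (108 weeks), EOS date and Death date".

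**The concern.** An AE onset and a death differ in one respect that matters for imputation. An AE can begin at any time during follow-up, whereas a death cannot precede a visit the subject attended. The trial records such visits by design: Section 2.1.1 keeps subjects who stop drug early in a post-treatment observation period, with 12-weekly visits until 108 weeks after randomization. Section 12.3 makes no use of that evidence.

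What is at stake is the split of deaths into treatment-emergent and later, a central safety display. The same subject can also carry two incompatible dates: for an undated death, Section 12.3 places the death at first dose while Section 5.1.6 places EOS at the last recorded visit.

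Elsewhere the SAP does use known evidence as a floor. In Section 5.4.2.3.1 a partial EDSS date may not fall before the day after the previous scheduled EDSS. In Section 5.2.2 a partial date of diagnosis may not precede first symptoms.

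**Working it through.** The plan gives no figure to reproduce, so the check applies its rules to assumed dates. Randomization and first dose are 1 Jun 2016 and EOT is 10 Jan 2017, so EOT + 15 days is 25 Jan 2017. Deaths are assumed to follow the main-CRF branch, since Section 5.5.3 takes them from the Death eCRF.

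| Case | Recorded death date | Last visit alive | True death (assumed) | Date under 12.3 | Flag under 12.3 | True status |
|---|---|---|---|---|---|---|
| A | none | 20 Mar 2018 | 5 Apr 2018, EOT + 450 | 1 Jun 2016 | treatment-emergent | later |
| B | 2017 | 20 Nov 2017 | 5 Dec 2017, EOT + 329 | 1 Jan 2017 | treatment-emergent | later |
| C | Jan 2017 | 28 Jan 2017 | 30 Jan 2017, EOT + 20 | 1 Jan 2017 | treatment-emergent | later |
| D | Mar 2017 | not needed | 20 Mar 2017 | 1 Mar 2017 | later | later |

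The imputed death precedes the last visit by 657 days in A, 323 days in B and 27 days in C. In C it also precedes the last dose by 9 days. In A, Section 5.1.6 gives EOS = 20 Mar 2018, so follow-up is 658 days against a true 674, while the death is dated to day 1.

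A month-only case at the boundary: last dose 20 Oct, alive on 20 Nov, death recorded as November. EOT + 15 is 4 Nov, so the month test passes. The death is dated 1 Nov and is treatment-emergent, although the subject was seen alive 16 days after the window closed.

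Furthest a death can lie from EOT and still be flagged:
- Day missing: EOT + 15 falls on the 1st and death on the 31st of that month, so 15 + 30 = 45 days.
- Day and month missing: EOT + 15 falls on 1 January and death on 31 December, so 15 + 364 = 379 days (one more in a leap year).
- Completely missing: no limit.

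Weight in the primary analysis: planned person-time is 1133 × 756 / 365.25 = 2345 years. One subject's entire 756 days is 1/1133, or 0.09% of it.

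With a floor at the last date known alive, the earliest admissible death dates become 20 Mar 2018 (A), 20 Nov 2017 (B) and 28 Jan 2017 (C). All are later than 25 Jan 2017, so all three deaths are classified as later, which agrees with the assumed truth. Case D does not change.

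**The case against.** The best defence is that this is a deliberate conservative convention, applied identically in both arms. Missing intensity becomes severe (5.5.2.2), missing relationship becomes related (5.5.2.3) and missing seriousness becomes serious (5.5.4). Section 9.10.2.1 also shows deaths overall and lists each one, so a misplaced death stays visible. Nothing in the SAP suggests that any death actually lacks a date. This stands where nothing else is known about the subject, and it limits the weight of the point. It does not justify a date that the trial's own visits contradict.

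Several stronger conclusions are tempting, and the SAP does not support them:

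- *Every partly dated off-drug death becomes treatment-emergent.* It does not. A month or year clearly after that of EOT + 15 days is classified correctly, as in case D.
- *Follow-up time is cut.* Not for an undated death, because Section 5.1.6 falls back on the last recorded visit. For a partial date it would follow only if Section 5.1.6 took the Section 12.3 imputation, which it does not say. On that assumption, a subject randomized 1 Mar 2016, alive on 15 Nov 2017, with death recorded as 2017, would have 307 days of observation (to 1 Jan 2017) instead of at least 625. With last dose on 1 Sep 2016 that death would still not be treatment-emergent, since 2017 is after the year of 16 Sep 2016.
- *The treatment period collapses to day 1 through Section 12.4.* This needs a missing EOT together with an undated death, and it needs Death date there to mean the imputed one, which is not stated. Section 12.4 also keeps its imputation out of the exposure variables.
- *AEs that ended before first dose become treatment-emergent.* This depends on an AE end date, which the SAP does not mention.

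**Conclusion.** The point holds for the classification and dating of deaths. Following Section 12.3 as written, a subject with documented visits after EOT + 15 days can be reported as a treatment-emergent death. The death date can be earlier than those visits and, if the death is undated, earlier than the subject's own EOS. The number of subjects is likely to be small and cannot be known from the SAP. Each one moves a death from the later category to the treatment-emergent one, which is visible when deaths are few. The primary ARR is not a reason to act, given the 0.09% bound per subject. For partial dates, the separate defect in Section 5.1.6 is that the rule for EOS is unstated, not that it is shown to be wrong. The conclusion rests on the text of Sections 12.3, 5.5.1 and 9.10.2.1 and on treating the Death eCRF as main-CRF data. The example dates are assumptions for illustration.

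**What to change.** Give death dates their own rule in Section 12.3:

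- partial date = max(lower limit, last date known alive from any visit or contact);
- completely missing date = last date known alive + 1 day, or the EOS date from Section 5.1.6.

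Derive treatment-emergence of deaths from that date. State in Section 5.1.6 that EOS uses the same floored date when the death date is partial, and in Section 12.4 that Death date means this floored date.

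The cost is a few sentences and minor programming, because the last recorded visit date is already derived for Section 5.1.6. The downside is a slightly less conservative count of treatment-emergent deaths.
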